⁹Beta-Human Chorionic Gonadotropin (HCG) testing will be conducted in all female patients, even pre-menarche, on blood collected at each scheduled visit until EoT. Pregnancy testing should be repeated every 4-6 weeks, i.e. at least at every visit and additionally at home or at a local laboratory / local doctor from Visit 4 until the end of the trial. If urine test is not acceptable to local authorities, a blood test will be done at a local laboratory. If applicable, urine dipstick pregnancy tests will be dispensed from Visit 4 until EoT, and use of pregnancy test diary card will be explained with the patient and/or parent(s)/legal guardian. Returned diary card will be reviewed with patient or parent(s)/legal guardian from Visit 5 until EoT, and training will be repeated as needed. The pregnancy test diary card will be used to support the record of the date and result of test(s) between consecutive visits. At the Follow-up Visit the pregnancy test will be conducted on urines (if acceptable), and test results will be documented in the patient's records. In case a positive test is reported the sponsor should be contacted immediately. Refer to [Section 3.3.4.1](#) for further instructions. Refer to [Section 5.2.7.2.3](#) for detailed information on event reporting in case of pregnancy.

¹¹Order of lung function measurements at Visit 2: 1. FVC followed by patient's rest; 2. D_{LCO}. After Visit 2 FVC measurements to be done at approximately the same time each visit, with reference time at Visit 2.

¹²Interactive Response Technology (IRT) should be notified upon obtaining informed consent, at Visit 1 at the latest. At Visit 6 IRT will assign open label treatment, and Part B will start once the first open label dose has been taken in the morning during the visit.

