¹³PK samples will be taken before drug administration at the clinic and at 6 timepoints post-dose (see [Flow Chart for PK blood sampling](#) for details). In exceptional cases, where extensive PK sampling is not possible and only in paediatric patients with an age < 12 years, a sparse sampling approach might be applied with a minimum blood sampling before (PTM of -0:05), 1 h (+/- 15 min) and 3 h (+/- 15 min) after nintedanib administration. Date and exact clock time of drug administration and blood sampling must be recorded in the eCRF. The patient and parent(s)/legal guardian will be provided (Visit 2 and Visit 6) with a PK diary card to support the record of the exact clock time of medication intake on the three days preceding PK sampling. At the beginning of the PK sampling visit (Visit 3 and Visit 7) the site personnel will check the PK diary card and confirm that the trial medication has been taken in the three days preceding the visit. If this is not confirmed, the visit will be rescheduled.

¹⁴At this visit drug accountability is to be completed only in case of dose reduction / increase.

¹⁵The PedsQL™ questionnaire should always be administered in a quiet place prior to any other visit procedure.

¹⁶Bone imaging (Magnetic Resonance Imaging (MRI) examination; if MRI cannot be performed, x-ray assessment) will be conducted in all patients who qualified for randomisation at baseline. Imaging follow-up will be conducted only in patients with open physes at 12 weeks, 24 weeks, 36 weeks, 52 weeks and every 24 weeks thereafter until the end of the study or closure of the physes. At EoT the MRI/x-ray should not be repeated if the last MRI/x-ray was conducted within 12 weeks in the first year, 24 weeks thereafter.

Dental examination (clinical) will be conducted in all patients who qualified for randomisation at baseline. Follow-up will be conducted in all patients at 12 weeks, 24 weeks, 36 weeks, 52 weeks and every 24 weeks thereafter until the end of the study. At EoT the dental examination will not be repeated if the last examination was conducted within 12 weeks.

Dental imaging (panoramic x-ray) will be conducted in all patients who qualified for randomisation at baseline. Follow-up will be conducted in all patients at 24 weeks, 52 weeks and every 48 weeks thereafter until the end of the study. At EoT the dental imaging should not be repeated if the last dental imaging was conducted within 24 weeks.

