If it's not possible to conduct the baseline bone imaging, and/or dental examination, and/or dental imaging on the day of Visit 2, the procedure can be done in the 2 weeks (until study day 15) immediately after the visit. If it's not possible to conduct the follow-up bone imaging, and/or dental examination, and/or dental imaging on the day of the visit, the procedure can be done in the week immediately before or after the visit. Please refer to the image acquisition guideline available in the ISF for details.

¹⁷After the individual patient's end of the trial the investigator should report only any occurrence of cancer, study treatment related Serious Adverse Events (SAEs) and study treatment related Adverse Event of Special Interests (AESIs) of which the investigator may become aware of by any means of communication, e.g. phone call. Those AEs should be reported on the BI SAE form, but not on the eCRF. Please see [Section.5.2.7.2.1](#).

¹⁸Patients who prematurely discontinue trial medication will be asked to remain in the study and return to all regularly scheduled visits until the end of the trial. For those patients who are unable to complete the scheduled visits, every attempt will be made to get information on vital status at 24 weeks after randomization, i.e. the time of the data cut-off for the primary analysis of safety, at 52 weeks and at the end of the trial.

In the event of force majeure or other disruptive circumstances (e.g. pandemic) the investigational plan as per this clinical trial protocol may not be feasible at a site. With the consent of the patient's parent(s)/legal guardian (and assent by the patient where applicable), sponsor and investigator may implement risk mitigation measures and modifications to CTP standard procedures as described in [Appendix 10.9](#). See also [Section 4.1.4](#), [Section 6.1](#) and ISF for details.

FLOW CHART FOR PK BLOOD SAMPLING

| Visit | Week (±days) | Time Point [hh:min] | CRF Time /PTM | Event |
|----------|-----------------|------------------------|------------------|---------------------|
| (Part A) | 2 (±3) | -0:05 ¹ | -0:05 | PK Blood |
| | | 0:00 | --- | Drug administration |
| | | 1:00 ² | 1:00 | PK Blood |
| | | 2:00 ² | 2:00 | PK Blood |
| | | 3:00 ² | 3:00 | PK Blood |
| | | 4:00 ³ | 4:00 | PK Blood |
| | | 6:00 ³ | 6:00 | PK Blood |
| | | 8:00 ³ | 8:00 | PK Blood |
| (Part B) | 26 (±3) | -0:05 ¹ | -0:05 | PK Blood |
| | | 0:00 | --- | Drug administration |

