Assessments on day of first open-label intake will be handled as follows:

- Assessments with time record: period is assigned based on time stamp (if time lies prior to open-label start then double-blind period; otherwise, open-label period)
- Assessments without time record: assigned to double-blind period, even if interruption prior to open-label start (if interruption longer than REP, then assessment falls into double-blind follow up period and thus, will not be evaluated anymore).
- Exception: AEs and concomitant medications with start date on day of open-label start will be assigned to the open-label period.

Further details will be specified in the ADS plan.

If in the double-blind period an interruption is not followed by a re-start of blinded treatment then this is counted as (early) discontinuation of the blinded treatment period. Over the whole trial, this will be counted as whole trial off-treatment period.

For safety analyses, data up to the end of the double-blind residual effect period / whole trial residual effect period / nintedanib residual effect period will be considered on-treatment.

For on-treatment efficacy analyses, data up to the day after last trial drug intake (included) will be considered.

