7.8 SAFETY ANALYSIS

7.8.1 Adverse Events

Adverse events will be coded using the current Medical Dictionary for Regulatory Activities (MedDRA) version in use at BI at the time of database lock. The analyses of AEs will be descriptive in nature.

All analyses of AEs will be based on the number of patients with AEs and NOT on the number of AEs. To account for the variable length of exposure to treatment in both study periods tables will be presented including count and percentage of patients with AE and the incidence rates of AEs with time at risk and rate per 100 patient years. Please refer to [Section 7.8.1.1](#) for further details on the derivation of time at risk and exposure-adjusted incidence rates.

Since this study consists of a double-blind, placebo-controlled part and an open-label part with nintedanib treatment only, three treatment periods will be used for analysis and definition of “treatment-emergent”:

- 1. Double-blind period:** Analyses of AEs will be presented by treatment group and overall. Only adverse events with onset or worsening on or after date of treatment start until end of double-blind period (defined as the day before first intake of open-label nintedanib or last double-blind drug intake + residual effect period, whichever is earlier) will be considered as treatment-emergent and will be included in the analysis. Adverse events will be counted under the treatment as randomized for the double-blind period.
- 2. Nintedanib exposure period:** Analyses of AEs will be presented by randomized treatment group and overall. All adverse events with onset or worsening on or after first intake of nintedanib (double-blind or open-label period) until last intake of nintedanib (double-blind or open-label period) + residual effect period will be considered as treatment-emergent and will be included in the analysis.

3. Over the whole-trial: Analyses of AEs will be presented by treatment group and overall. All adverse events with onset or worsening on or after date of treatment start until last drug intake + residual effect period will be considered as treatment-emergent and will be included in the analysis. Adverse events will be counted under the treatment as randomized for the double-blind period.

In case an AE starts on first day of open-label treatment, it is assigned to the open-label period (and not to the double-blind period).

For further details on summarization of AE data, please refer to ([8](#), [17](#)).

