7.8.1.3 Adverse events with additional information collection

Diarrhea, bleeding and ILD are AEs with additional AE-specific information collected on the eCRF. These are investigator reported on the eCRF and will be identified using this information for this analysis. That is if the diarrhea information has been completed for an adverse event then the adverse event will be considered as diarrhea for this analysis regardless of subsequent MedDRA coding of the verbatim term. Likewise, if the bleeding information has been completed for an adverse event then the adverse event will be considered as bleeding for this analysis regardless of subsequent MedDRA coding of the verbatim term. The same applies to ILD.

The frequency of patients with AEs with additional information collection will be summarized by treatment group and overall, primary SOC and PT and separately for diarrhea, bleeding and ILD. The additional information collected will also be summarized at the AE level (occurrence level) rather than at the patient level separately for diarrhea, bleeding and ILD. These analyses will be provided by analysis periods and treatment group and overall, where applicable.

For the time to first onset of diarrhea, bleeding or ILD, respectively, Kaplan-Meier plots by treatment will be created taking into account the respective data over the whole trial. Kaplan-Meier plots of the double-blind period and the nintedanib exposure period will be created as well. The same censoring rules as for time to first liver enzyme elevation trial will be used, see [Section 5.4.4.1](#) for details.

7.8.1.4 Pathological findings of epiphyseal growth plate on imaging, on dental examination or dental imaging

Adverse events identified based on imaging or dental examination will be reported in the Adverse Event page of the eCRF and will be listed in the standard AE tables and listings.

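### Findings from a week-24 bone or dental assessment done and dated at Visit 6 or later leave the double-blind AE/AESI tables and, in placebo patients, enter the nintedanib-exposure tables

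*SAP*

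**What the plan says.** **Where the events go.** SAP 7.8.1.4 states that "Adverse events identified based on imaging or dental examination will be reported in the Adverse Event page of the eCRF" and appear in the standard AE tables and listings. It adds nothing on how they are assigned to a period.

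**How events are assigned.** SAP 7.8.1 ends the double-blind period on the day before first open-label intake, or at last blinded dose plus the 28-day residual effect period if that is earlier. For an AE starting on the first open-label day it says "it is assigned to the open-label period (and not to the double-blind period". SAP 6.1 repeats this as an explicit exception: "AEs and concomitant medications with start date on day of open-label start will be assigned to the open-label period". The general rule beside it runs the other way: "Assessments without time record: assigned to double-blind period". The nintedanib-exposure tables take "All adverse events with onset or worsening on or after first intake of nintedanib".

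**When the assessments happen.** Protocol Flow Chart footnote 12 places the first open-label dose at Visit 6: "Part B will start once the first open label dose has been taken in the morning during the visit". Footnote 16 schedules bone imaging (open physes only) and dental examination at weeks 12 and 24 within Part A. For panoramic x-ray it says "Follow-up will be conducted in all patients at 24 weeks, 52 weeks and every 48 weeks thereafter". If the visit day is not possible, "the procedure can be done in the week immediately before or after the visit".

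**What these events are.** Pathological bone-imaging findings and stunted growth on dental imaging are AESIs (Protocol 5.2.7.1.4). SAP 7.8.1 plans a double-blind AESI table by treatment group.

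**The concern.** Structural bone or tooth changes found at week 24 developed during the preceding 24 weeks of randomised treatment. A same-day dose cannot plausibly have caused them. Yet the AE rule takes such a finding out of the blinded comparison in both arms. In a placebo patient it then counts as treatment-emergent on nintedanib, with onset on nintedanib day 1.

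Protocol 3.2 justifies the placebo arm by the need to interpret AE reports, and Table 1.4.2:1 describes the tooth changes in animals as irreversible. A nearly empty double-blind row for stunted growth could be taken as reassurance when the main scheduled look in Part A was left out of the table. The nintedanib-exposure tables could in turn show findings that arose on placebo.

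**Working it through.** **1. The plan's own days.** Week 24 is day 24 × 7 + 1 = 169, as in the SAP 6.7 tables. For bone imaging and dental examination, (85 + 169)/2 = 127 and (169 + 253)/2 = 211, so the week-24 window is days 128–211, matching Table 6.7: 4. For dental imaging, the baseline window ends on day 15 and (169 + 365)/2 = 267, so the window is days 16–267, matching Table 6.7: 5.

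**2. The AE period rules applied to the permitted scan days.** Assume the first open-label dose is on day 169 and AE onset is the scan date. The scan may be done from day 169 − 7 = 162 to day 169 + 7 = 176, which is 15 days.

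| Onset day | Double-blind AE/AESI tables (both arms) | Nintedanib-exposure tables (placebo-randomised) |
|---|---|---|
| 162–168 (7 days) | in | out |
| 169, as scheduled | out | in |
| 170–176 (7 days) | out | in |

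So 7 of the 15 days stay double-blind and 8 do not. These are counts of days, not shares of scans; the visit day is the default and the adjacent weeks are the fallback. All 15 days lie inside both week-24 windows from step 1, so the secondary imaging endpoints still place the scan at week 24.

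**3. Scheduled post-baseline assessments in Part A whose findings stay in the double-blind AE tables, with week-24 procedures done and dated at Visit 6.**
- Panoramic x-ray (week 24 only): 0 of 1.
- Bone image (weeks 12 and 24): 1 of 2.
- Dental examination (weeks 12 and 24): 1 of 2.

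An early end-of-treatment visit would not normally add a panoramic x-ray, because footnote 16 omits it when one was taken within 24 weeks.

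**4. The onset date.** Protocol 8.3.1 makes it mandatory, but neither document defines it for a finding detected on imaging. The scan date gives step 2. A later central-read date could also move scans done before Visit 6. A back-dated onset would keep the event double-blind.

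**5. Size, for illustration only.** With the planned 20 and 10 patients, each placebo finding that moves adds 1/10 = 10 points to the placebo-randomised column of the nintedanib-exposure tables and 1/30 = 3.3 points overall. Let *f* be the share of week-24 assessments done before Visit 6 and dated to the scan, assumed 0, 25% or 50%.
- Panoramic findings kept double-blind = *f* = 0%, 25%, 50%. At an assumed true rate of 20% on nintedanib (0.20 × 20 = 4 patients), the table shows 4*f* = 0, 1 or 2.
- Bone findings kept = 0.5 + 0.5*f* = 50%, 62.5%, 75%, if half are first seen at week 24.

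The documents give neither *f*, nor the 20% rate, nor the one-half.

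**The case against.** **The comparison exists elsewhere.** SAP 5.2.2.1 and 5.2.2.2 report these findings cumulatively over 24 weeks, by randomised arm under the SAP section 7 default, using central reads for the images. The whole-trial AE and AESI tables also count them under the randomised arm. This stands: no data are lost. It does not fully replace the double-blind AESI row. The dental endpoint pools stunted growth with accelerated growth, extra or impacted teeth, cysts, other findings and dental-examination findings. The whole-trial tables add open-label time, when both arms take nintedanib.

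**Not every week-24 finding moves.** A reader might infer that the stunted-growth row must read zero against zero whatever the drug does. The documents do not support that. Scans done before the visit and dated to the scan, back-dated onsets, and scans within 28 days of the last blinded dose in patients not yet on open-label drug all remain double-blind.

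**The rule is deliberate.** A reader might also infer that the SAP contradicts itself, since an untimed same-day scan is double-blind while its AE is open-label. SAP 6.1 labels the AE rule an exception, so the difference is intended. SAP 6.6.2.4, which expects no imaging change within two weeks of starting treatment, concerns which image may serve as baseline. The Visit 6 adjustment in SAP 6.7 concerns visit windows. Neither is an AE attribution rule. What remains is that a reasonable general exception was not adapted for findings that take weeks or months to form.

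**Some detail is out of sight.** Site instructions on onset dates, the ADS plan and the sponsor's AE guidance are not in the two documents. That limits certainty about how many events move. The open-label-day rule itself is stated in full.

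**Little hangs on it.** Safety analysis is descriptive, and Protocol 4.1.2 requires treatment interruption and SMC review for bone-imaging findings and stunted dental growth. Individual patient protection is therefore unaffected; the weakness is in how the aggregate tables would be read.

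**Conclusion.** The point holds for patients who start open-label drug on schedule and whose week-24 assessment is done and dated on that day or later. Their findings leave the double-blind AE/AESI tables and, if they were on placebo, are counted under nintedanib exposure. The stunted-growth row is the most exposed, because Part A schedules only one post-baseline panoramic x-ray; bone-imaging and dental-examination findings keep their week-12 look.

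The conclusion rests on the stated date rules and visit schedule, and on an onset date no earlier than the scan. The effect on the primary any-AE count is probably small. It would be wrong to infer that safety data are lost or that the randomised comparison at week 24 is unavailable. This is a cheap improvement to the tables.

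**What to change.** Keep the date-based tables and remove no investigator-reported event. In SAP 7.8.1.4, with a cross-reference in 6.1 and 7.8.1:

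- Add a supplementary double-blind AE/AESI table by randomised arm that includes AEs whose source is the week-24 bone or dental assessment, up to 7 days after the first open-label dose.
- In the nintedanib-exposure tables, keep such AEs for placebo-randomised patients, but footnote them and list them as *first seen on week-24 assessment*.

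The cost is one SAP paragraph, one table, one footnote and a flag linking the AE to the week-24 safety read or dental eCRF page. No new data are needed. The drawback is that a placebo patient's event can appear in both the supplementary table and the nintedanib-exposure tables; the footnote should say so.

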7.8.2 Laboratory Data

7.8.2.1 Standard laboratory analyses

The analyses of laboratory data will be descriptive in nature and will be based on BI standards (21). The variables to be recorded are listed in [Table 7.8.2.1: 1](#) and [Table 7.8.2.1: 2](#) below (see also Section 5.2.3 of the CTP).

Table 7.8.2.1: 1 Safety laboratory tests at regular site visits

The laboratory tests at regular site visits will include:

Category	Laboratory test
Haematology	Red blood cell count (RBC) Haemoglobin (Hb) Haematocrit (Hct) Mean corpuscular volume White blood cell count including differential count Platelet count
Biochemistry	Aspartate aminotransferase (AST) Alanine transaminase (ALT) Gamma-glutamyl transferase (GGT) Alkaline phosphatase (ALK) Creatine kinase (CK) Lactate dehydrogenase (LDH) Total protein Total bilirubin Creatinine Glucose (non fasting, V1 and V2 only) Uric acid Thyroid stimulating hormone β-HCG (at all visits requiring blood sampling for laboratory tests –in all and only female patients)*

Table 7.8.2.1: 1 Safety laboratory tests at regular site visits (continued)

Category	Laboratory test
Electrolytes	Sodium Potassium Calcium Chloride Inorganic phosphorus
Coagulation	International normalized ratio (INR) Activated partial thromboplastin time (aPTT) Prothrombin time (PT)
Urinalysis	pH, glucose, erythrocytes, leukocytes, protein, nitrite (semi-quantitative measurements; -, +, ++, +++)

*Pregnancy test is required in all female patients every 4-6 weeks (in Poland: every 4 weeks), either at home or at site. β -HCG test on blood will be conducted at all visits on blood collected for laboratory tests. Locally provided urine dipstick pregnancy tests will be dispensed for use between clinic visits starting from Visit 4.

Table 7.8.2.1: 2 Safety laboratory tests at intermediate ‘a’-visits

The laboratory tests at intermediate ‘a’-visits will include:

Category	Laboratory test
Biochemistry	Total protein, creatinine, electrolytes and liver function (AST, ALT, GGT, alkaline phosphatase, and total bilirubin)
Urinalysis	pH, glucose, erythrocytes, leukocytes, protein, nitrite (semi-quantitative measurements; -, +, ++, +++)

As described in Section 7.2.5 of the CTP, laboratory data will be analyzed both quantitatively as well as qualitatively. The latter will be done via comparison of laboratory data to their reference ranges. Values outside the reference range as well as values defined as clinically relevant will be summarized. Treatment groups will be compared descriptively with regard to distribution parameters as well as with regard to frequency and percentage of patients with abnormal values or clinically relevant abnormal values.

Data will be received from a central laboratory, the respective reference ranges will be provided in the ISF.

For INR measurements, no reference range is transmitted by the central laboratory, because the central laboratory does not have information on concomitant medication taken by the subjects, and the reference range for INR depends on whether a subject is taking anticoagulants. The reference ranges for INR will therefore be imputed with 0.8 for the lower limit of normal (LLN) and with 1.2 for the ULN, which correspond to the

reference range defined by the central laboratory for subjects not taking anticoagulants and which is more conservative than the range for subjects taking anticoagulants (LLN=2, ULN=3).

Analyses of laboratory variables will be displayed by treatment and overall for the double-blind period, for the nintedanib exposure period and over the whole trial; please refer to [Table 6.7: 1](#) for time windowing definition.

